	implementation assessed through a trial specific checklist completed by
	observers, reliability of teacher and school reporting of implementation
	through KiVa lesson observation and teacher fidelity rating measures
	completed by observer, and in-depth interviews conducted at eight
	intervention schools
	4. Intervention mechanisms and factors influencing implementation will be
	explored through focus groups and interviews with pupils and parent/carers
	of KiVa schools and through observation of lesson and school-wide delivery
	5. Schools' usual antibullying practices and will be determined by obtaining a
	copy of each school's antibullying policy, through completion of a trial
	specific proforma and through discussion with the schools' Headteacher
Intervention	KiVa (meaning 'nice' in Finnish and, 'Ki' and 'Va' beginning the Finnish words
	for 'against bullying') is an antibullying programme developed in Finland where
	it is has now been scaled up extensively. In this trial, KiVa will be delivered to
	KS2 pupils in intervention schools over one academic year. The core KiVa
	curriculum involves the delivery of class lessons (fortnightly or monthly
	depending on the school's timetable) delivered by class teachers who have
	received KiVa training from the school KiVa coordinator. Lessons cover
	definition of bullying, understanding and reflecting on emotions, group
	interactions processes, the mechanisms and consequences of bullying, group
	pressure, they also describe how bullying is affected by bystander behaviours
	and how to reduce different types of bullying, including cyberbullying, and
	support fellow pupils. KiVa lessons map onto over 50% of Welsh Personal Social
	Education (PSE) and English Personal Social Health Education (PSHE)
	curriculum. Confirmed incidents of bullying are addressed by the school's KiVa
	team using the KiVa scripted strategies and forms. KiVa is also implemented
	and visible schoolwide through whole school assemblies, KiVa vests worn by
	staff at break times to identify them as part of the school's KiVa team, and KiVa
	posters to increase the presence of the programme at the school.

Figure 1. Stand Together trial flow diagram

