3.2.2 The trial

This trial will investigate whether implementation of the KiVa programme over one academic year is more effective in reducing reported bullying in UK primary schools than usual practice. One hundred and sixteen non-fee-paying primary schools (approximately 12 800 pupils) from four geographical areas (North Wales and Cheshire, the West Midlands and South East and South West England) will be recruited to the trial. Schools will be randomly split into two groups; half (n = 58) will implement KiVa with Key Stage 2 (KS2) pupils aged 7-11 years and half (n = 58) will form a UP group and continue with their usual antibullying practices. School size and level of deprivation as measured by Free School Meal (FSM) eligibility will be considered when allocating schools to a group. KiVa has dedicated 45-minute fortnightly lessons for pupils in years 3-6 (ages 7-11), posters, online games to play at home and/or school, whole school assemblies, parent information, designated trained staff to deal with confirmed bullying incidents and set procedures for use when bullying occurs. Class lessons teach an understanding of children's own and others' emotions and how to stand up against bullying and support victims.

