3.2.3 Methods

Before the start of the 2020/21 academic year, KS2 pupils will complete questionnaires about their experience of bullying at school, how they feel about school and their general wellbeing. KS2 teachers will complete questionnaires about the behaviour of each pupil in their class, their confidence in dealing with bullying and the mental wellbeing. Pupils and teachers will complete these questionnaires towards the end of the 2020/21 academic year (May/June 2021). The study will be reporting whether there is a

reduction in the proportion of pupil self-reported bullying victimisation from the start to the end of the academic year and whether this reduction is greater within schools that delivered KiVa compared to schools that continued with their usual practice. To learn more about how KiVa lessons were delivered, the factors that influenced delivery, how it was delivered schoolwide and how it was received by participants, researchers will conduct interviews and focus groups with staff, pupils and parents in schools that delivered KiVa. Interviews will also be conducted with school staff from the control group to learn more about usual antibullying practices in UK primary schools. In addition, the cost of KiVa will be calculated and weighed up against any benefits in terms of reduced reported bullying, pupil quality of life and use of services related to bullying.

Trial findings will be disseminated through policy briefings, in press-releases, social media updates, via the creation of short audio-visual clips for schools and children and published in peer-reviewed academic journals and conference presentations.

4 Background

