5.1 Primary objective

The aim of this trial is to investigate whether implementation of the KiVa programme over one academic year is more effective in reducing self-reported rate of bullying victimisation among pupils aged 7-11 years in UK primary schools than usual practice at 12 Month follow-up.

It is hypothesised that after one school year of implementation, KiVa will produce a 4% absolute reduction, or 22% relative reduction, in the proportion of pupil self-reported bullying victimisation from baseline.

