5.4 Primary outcome measures

The primary outcome is the proportion of pupils self-reporting bullying victimisation and will be measured using the OBVQ [25]. In both the intervention and UP arms at Baseline and at 12 Month follow-up. This questionnaire measures the rate of total and different forms of bullying, including verbal, physical, relational and cyber-bullying. The OBVQ [25] has been used both in Finland and internationally for KiVa trials, enabling comparison across trials. The item that will be used to assess the primary objective is item 4, "How often have you been bullied at school in the past couple of months?" to which pupils may select one of the following responses: "I haven't been bullied at school in the past couple of month = 0", "it has only happened once or twice = 1", "2 or 3 times a month = 2", "about once a week = 3" or "several times a week = 4". The responses will be dichotomised so that a response of 2-4 will indicate bullying victimisation and responses 0-1 will indicate no bullying victimisation.

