11.1 Core curriculum

The core curriculum targets pupils in Years 3 and 4 (unit 1), and Years 5 and 6 (unit 2). Each unit contains ten structured ninety-minute lessons, typically split into two 45- minute lessons, delivered fortnightly throughout the school year. Lessons describe how bullying is affected by bystander behaviours and cover understanding and reflecting on emotions, group interactions processes, the mechanisms and consequences of bullying, group pressure and how to reduce different types of bullying, including cyberbullying, and support fellow pupils. The curriculum aims to create an emotionally and socially supportive setting that encourages pupil engagement via oral presentations, role-play, videos, group work, and whole class activities. KiVa covers over half of the PS(H)E provision in Wales and England. Online games to support learning can be played at home and/or school. Class lessons for all four years of KS2 pupils (aged 7-11 years) will be delivered by KS2 class teachers.

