14.3 Sample size

The sample size calculation is based on data from the roll-out of KiVa in Finland where a reduction from 18% to 14% in rates of victimisation was observed [37]. A similar baseline rate of victimisation of 18% was obtained from a current UK based pre-post study of 41 schools [23]. An individual pupil level analysis correcting for clustering by school will be undertaken. To achieve a reduction from 18% at baseline to 14% (4% absolute reduction, 22% relative reduction), a total of 3,520 pupils are required to power an

individual level trial at 90% and a 5% significance level. This reduction equates to an effect size (odds ratio) of 1.35 which is of public health significance and is broadly in line with other effect estimates from KiVa and the wider literature on bullying and victimisation. The pooled odds ratio found in Ttofi's and Farrington's 2018 systematic review of bullying and victimization was 1.24 [6] and our effect size is midrange of other relevant KiVa studies which range from 1.22 [11] to 1.47 [8]. The study will take account of clustering. In the Finnish study the school level intra-cluster correlation (ICC) for the comparison of KiVa and UP in self-reported victimization was 0.02 at the 12-month follow-up. An average cluster size of 111 pupils in years 3 to 5 is assumed. This is based on recruiting children from 3-year groups (years 3, 4, 5) with an average 27.8 pupils per class (based on 2018 KS2 figures from English schools), and an average 1.34 classes per year (based on the data from our UK KiVa pilot study where half of recruited schools had more than one class per year).

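### Table 1 opens the primary-outcome survey in April 2021, while KiVa is still being delivered and earlier than other sections say, so lesson exposure at follow-up depends on each school's survey date

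*Protocol*

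**What the plan says.** **Lessons.** Section 11.1: "Each unit contains ten structured ninety-minute lessons, typically split into two 45- minute lessons, delivered fortnightly throughout the school year". Section 3.2.2 agrees on length and spacing: "KiVa has dedicated 45-minute fortnightly lessons for pupils in years 3-6 (ages 7-11". The intervention row of the Synopsis is looser, leaving the frequency to the school's timetable: "curriculum involves the delivery of class lessons (fortnightly or monthly".

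**Delivery and follow-up dates.** Table 1 places randomisation in May-June 2020, delivery in September 2020 to June 2021, and the Month 12 follow-up, including the pupil and teacher questionnaires, in April to June 2021. Section 3.2.3 is narrower: "Pupils and teachers will complete these questionnaires towards the end of the 2020/21 academic year (May/June 2021". Section 10.2 puts the second measurement 12 months after randomisation. Section 6 says effectiveness is assessed 24 months after randomisation. The Synopsis gives the intervention duration as 12 months.

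**Claim and measure.** Section 5.1: "It is hypothesised that after one school year of implementation, KiVa will produce a 4% absolute reduction, or 22% relative reduction". The primary item (section 5.4) asks "How often have you been bullied at school in the past couple of months". Section 15.1 analyses by intention to treat, whatever the adherence.

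**The concern.** The questionnaires that carry the primary outcome may be taken at any point in a three-month window that lies wholly inside the delivery period. No stated rule links a school's survey date to the lessons it has delivered, or keeps survey dates comparable between arms. Two KiVa schools on the same lesson timetable could differ by several sessions at the primary outcome only because a hub visited one in early April and the other in late June.

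If lessons contribute to the effect, early surveys may pull the estimate towards the null. A lesson count taken over the full year would also overstate what pupils in early-surveyed schools had received when they answered, which matters because section 5.6.4 relies on fidelity data to interpret the result. The protocol also gives hubs several incompatible descriptions of when follow-up occurs.

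**Working it through.** **1. The dates side by side**

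| Source | Timing of follow-up or intervention | Consistent with May/June 2021 follow-up? |
|---|---|---|
| Section 3.2.3 | Questionnaires in May/June 2021 | Yes |
| Section 10.2 with Table 1 | Randomisation May-June 2020, plus 12 months = May-June 2021 | Yes |
| Table 1 | April-June 2021; April is 10-11 calendar months after randomisation | April is not |
| Section 6 | 24 months after randomisation = May-June 2022 | No |
| Synopsis | 12-month intervention; Table 1 allows September to June = 10 months | Duration mismatch only |

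From 1 April to the end of June is three months, so an April survey can precede the end of delivery by that much.

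**2. Length of the lesson schedule**

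Ten lessons × 2 = 20 sessions. First to last is 19 gaps × 2 weeks = 38 weeks. From 1 September 2020, with no holidays at all, the 20th session falls in the week of 24 May 2021. From 7 September it falls in the week of 31 May.

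**3. Sessions delivered by a given date**

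Sessions = floor(teaching weeks elapsed / 2) + 1, capped at 20. From 1 September 2020:

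- To 1 April 2021: 212 days = 30.3 weeks, floor(15.1) + 1 = 16.
- To 1 May: 242 days = 34.6 weeks, floor(17.3) + 1 = 18.
- To 30 June: 302 days = 43.1 weeks, floor(21.6) + 1 = 22, capped at 20.

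The protocol gives no term dates. As an assumption I take seven holiday weeks: one in October, two at Christmas, one in February, two at Easter (in April) and one at the end of May. Four fall before 1 April, six before 1 May and seven before 30 June. From 1 September this gives:

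- To 1 April: 26.3 weeks, 14 sessions.
- To 1 May: 28.6 weeks, 15 sessions.
- To 30 June: 36.1 weeks, 19 sessions.

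A 7 September start lowers most counts by one. A calendar count gives:

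| Survey date | No holidays | Assumed holidays |
|---|---|---|
| Start of April | 15-16 of 20 | 13-14 of 20 |
| Start of May | 17-18 | 14-15 |
| End of May | 20 | 16-17 |
| End of June | 20 | 18-19 |

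The monthly option in the Synopsis leads to the same place. Ten monthly 90-minute lessons from September end in June, with 7 of 10 given by the end of March.

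**4. Recall period**

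Because the item looks back a couple of months, a survey at the start of April describes roughly February and March. On 1 February the count is 10-11 sessions (153 days from 1 September = 21.9 weeks, giving 11; less three holiday weeks, 18.9, giving 10). It rises to 13-16 by the end of March.

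**5. What attenuation could cost (illustration only)**

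Section 14.3 says "a total of 3,520 pupils are required to power an" individual-level trial of 18% against 14% with 90% power. This reproduces: (1.960 + 1.282)² × (0.18 × 0.82 + 0.14 × 0.86) / 0.04² = 10.507 × 0.268 / 0.0016 ≈ 1,760 per arm, or 3,520 in total.

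With 57 schools per arm, 111 pupils less 10% = 99.9 and an ICC of 0.02, the design effect is 1 + 98.9 × 0.02 = 2.978. The effective n is 57 × 99.9 / 2.978 ≈ 1,912 per arm. Power at the full 4-point difference is 0.92 (0.90 stated).

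If the effect were proportional to sessions delivered and every school were at the same fraction, power would be 0.86 at 90%, 0.76 at 80% and 0.64 at 70%. The protocol gives no dose-response, and schools would be spread over the window, so these figures show direction only. They do not forecast the trial's power.

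**The case against.** A reader might infer that the trial will measure a part-delivered programme and so cannot answer its primary objective, or that a null result could not be told apart from incomplete exposure. The protocol does not support either inference.

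- **Timing.** Sections 3.2.3 and 10.2 both point to May-June 2021, so April in Table 1 is the outlier. That column also covers consent, linkage and interviews. This stands, but the questionnaire row sits under the same column with no narrower date, so a hub working from Table 1 may start in April.
- **The objective.** Section 5.1 concerns implementation over one academic year, analysed by intention to treat. It does not promise a finished curriculum. Lessons run all year, so any survey within that year overlaps the last ones. This stands.
- **Other components.** The indicated actions (section 11.2) and school-wide elements (section 11.3) are not tied to the number of lessons completed. This stands, and it limits how far lesson count can stand for dose.
- **Fidelity data.** Teachers record every lesson in all intervention schools (section 5.6.4.1), and section 5.6.4 plans to relate delivery to outcomes. A null result can therefore be examined against coverage. This stands, provided that lessons are counted to the survey date.
- **The schedule is inferred.** The split into 45-minute sessions is described as typical. A full 90-minute lesson each fortnight would finish in January or early February. That reading fits poorly with lessons spread over the school year and with section 3.2.2, so 20 fortnightly sessions is the better reading, though not a fixed rule.

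**Conclusion.** The point holds as a problem of inconsistent timing and avoidable variation in exposure. Table 1 permits the primary outcome to be taken up to three months before delivery ends and 10-11 months after randomisation, against sections 3.2.3 and 10.2. The 24 months in section 6 fits none of these.

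On the typical fortnightly schedule, a school surveyed at the start of April has had at most 16 of 20 sessions. This upper limit needs no holiday assumption. With four assumed holiday weeks by then it is 13-14. By the end of June it is 18-20. Early surveys may therefore attenuate the effect in KiVa schools, by an amount that the protocol does not allow anyone to estimate.

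The conclusion rests on reading section 11.1 as 20 sessions and on a start in the first days of September. It does not extend to saying that the objective is unanswerable: schools surveyed in late June would have had 90-100% of their lessons, and the estimand is a year of implementation, not a completed curriculum.

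**What to change.** - In Table 1, give the pupil and teacher questionnaires their own window of May/June 2021, matching sections 3.2.3 and 10.2.
- Correct the 24 months in section 6 to 12 months after randomisation, and the 12-month intervention duration in the Synopsis to one academic year.
- Survey schools as late in the May/June window as feasible, with dates balanced by arm within area and stratum. A survey at the start of May would still find only about 14-18 of 20 sessions delivered, so moving the window alone does not settle the matter.
- In the fidelity analysis, count lessons up to each school's survey date as its exposure. The per-lesson records already planned are the natural source.

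The cost is protocol wording and fieldwork planning. The real downside is a shorter survey period for each hub.

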11.2 Indicated actions

Each school will have a dedicated KiVa team (2-3 staff members) who will be trained by accredited KiVa trainers to address confirmed bullying incidents using the KiVa structured and scripted process. Bullying incidents will be recorded in a designated KiVa logbook.

11.3 School-wide elements

Some intervention components are delivered across the whole school alongside delivery of the KiVa lesson curriculum to KS2 pupils. This includes universal actions to ensure that the entire school staff are knowledgeable about the KiVa programme and how it operates in the school. All school staff must know how to make a referral to the KiVa Team. The programme is introduced to all staff, parents, and pupils and is visible across the school with high visibility vests for break time supervisors (to identify the school's KiVa team), posters (to increase the presence of KiVa at the school) and a parent's guide. School launches are provided for staff and parents to inform and prepare them for the programme.

11.4 KiVa training

The Bangor based Children's Early Intervention Trust (CEIT) charity holds the UK KiVa dissemination contract and will co-ordinate KiVa training. KiVa materials, manuals, and online access are provided at the training (an annual re-registration fee payable to KiVa Finland is required for continued access to the online resources). There will be at least one accredited trainer per hub (both Warwick and Bangor already

have trainers and interest has already been generated at the two other sites). Two school staff members will attend a two-day training (ideally the KiVa coordinator and the KiVa Team lead) and co-ordinate the programme launch with all school staff, pupils and parents. They will train KS2 teachers in lesson delivery and all school staff in methods of reporting suspected bullying incidents. The KiVa team lead will train all school staff in methods of reporting suspected bullying. KiVa team members will ensure that someone is rapidly available, to assess referrals against KiVa bullying criteria and, if confirmed, to implement the indicated programme components including working with the victimised child's class teacher. Some referrals may not meet the definition of bullying and will be dealt with according to normal school procedures for disputes, misunderstanding and accidents.

12 Trial procedures

A summary of trial procedures is shown in Table 1 (Page 39).

12.1 Baseline data collection

12.1.1 School demographic data

For each school, postal code and school-level data including number of pupils enrolled, ethnicity and FSM eligibility will be obtained through publicly available online databases such as http://statswales.gov.wales and https://www.gov.uk/search/research-and-statistics. Number of KS2 pupils enrolled at the school, gender (class level) and special educational needs status (SENS) will be obtained from the schools.

12.1.2 Contacts with the school regarding bullying

The school will provide information about the frequency of contact the school has had with pupils and/or other parent/carer regarding bullying.

12.1.3 Usual antibullying practice

Headteachers will complete a proforma containing questions about the school's usual antibullying practices. The proforma will collect information about bullying prevention measures (lessons, assemblies, programmes), strategies for dealing with bullying incidents (whether incidents are recorded, who is involved, whether incidents are followed up), staff antibullying training and parental involvement in incidents of bullying. A copy of all schools' antibullying policy will be obtained online or from the

Headteacher. To supplement the written data, the researcher will obtain more information through discussion with the Headteacher.

12.1.4 Pupil and teacher self-report questionnaires

Research assistants will attend schools to administer and collect pupil and teacher questionnaires. Prior to data collection, the school will note the pupils whose parent/carer returned a 'right to object' form and will have made alternative arrangements to allow these pupils to remain in the data collection environment to avoid embarrassment. Pupils whose parent/carer did not return a 'right to object' form will complete self-report questionnaire data (OBVQ [25], HIFAMS [31] and CHU-9D [26]) on school grounds. Ideally the researcher will read the questionnaires aloud to the whole class to maximise completion rates and data quality. This approach will be field tested prior to data collection to determine feasibility. If it is not feasible, pupils will complete their questionnaires by themselves 'under exam conditions' and the field workers will walk around the room to identify those who are experiencing difficulty. The research assistant will discretely offer help to these participants. Irrespective of the approach, researchers will ensure not to use leading language or appear to be monitoring the participants' response. School staff may choose if they wish to be present during data collection. KS2 teachers will complete the TSDQ [27], CBSES [28], WEMWBS [29] and MBI-ES [30] at the same data collection timepoint.

Teachers and pupils will ideally complete CRFs electronically using encrypted tablet devices. There will be enough tablets for each child so that questionnaires can be completed as a class. However, if technical issues arise and prevent electronic data collection, paper CRFs will be completed instead. Completed paper questionnaires will be reviewed by field workers at each site as part of quality control. They will then be transferred to the CTR using Royal Mail Special Delivery post where they will be scanned and stored in pseudonymised form, using participant identification numbers (PID) and a non-unique identifier e.g. initials. PIDs and identifiable information i.e. participant names, will be stored in separate files. Both files will be stored in secure password protected folders.

